Participant's Review of Inclusion/Exclusion Criteria: Prospective participants will initially review general inclusion and exclusion criteria about the study on the recruiting materials where there is contact information to contact a researcher for more detailed information about the study.

Interested individuals will be screened through a phone screen script. Their continued interest in the study confirms that they have met (via self-report) basic inclusion/exclusion criteria.

Administration of Consent Form: When the Consent form is administered, participants will have already acknowledged that they have met the above criteria and have expressed continued interest in participating in the study. If, at that time, they feel that they do not meet these criteria, or have specific questions about these criteria, they will be asked to inform the research team member administering the consent form. If they again meet these criteria to the best of their knowledge, a second set of study screening procedures will be administered to evaluate whether or not they qualify for the study. All of the remaining screening and study procedures described hereinafter will be administered only if the participant has provided consent to participate (i.e., signed the consent form).

It is an eleven day study with four follow-up sessions: 1 week, 4 weeks, 12 weeks and 24 weeks after the last day of stimulation.

Session 1: Pre-tDCS Assessment (approximately 3 hours)

Assessment: At [name]'s lab, The following questionnaires/tests will be administered:

- 1. VAS. The Visual Analogue Scale
- 2. MFIS. Modified Fatigue Impact Scale
- 3. PSQI. Pittsburgh Sleep Quality Index
- 4. BDI. Beck Depression Inventory
- 5. PCS. Pain Catastrophizing Scale
- 6. MGPQ. McGill Pain Questionnaire
- 7. PVAQ. Pain Vigilance and Awareness Questionnaire

In addition, changes in electrophysiological brain activity will be measured using resting-state EEG.

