Resting state EEG. The EEG procedure is a non-invasive technique that will record brain electrical activity while the participant sits quietly in a chair for 5 minutes with their eyes are closed. In order to do that, a cap with 64 electrodes will be placed on the scalp. The cap is similar to a loose nylon swim cap. The cap will be placed on the participant's head and then a small amount of a salt water mixture will be added to each electrode from the outside of the cap. The cap placement will take up to 30 minutes. This is a common clinical procedure carried out in neurology.

Session 2-10: tDCS stimulation (approximately 45 minutes)

tDCS Stimulation - Participants will be randomly assigned to two different groups after they have finished assessment: the first group will receive real tDCS targeting the occipital nerve field. This group will receive 20 minutes of stimulation targeting the occipital nerve field area consisting of a current of 1.5mA. The second group (sham, or control, group) receive the same procedure for tDCS but with no delivery of electrical current. For both groups, the stimulation current will gradually ramp up to 1mA during the first 60 seconds of stimulation but the current will only persist for real tDCS group.

Session 11: tDCS stimulation + Immediate Post-tDCS Assessment (approximately 3.5 hours)

tDCS Stimulation - Participants will receive tDCS for 20 minutes (1) at 1.5 mA targeting the occipital nerve field area, or

Last Revised 01/2016 Page 14 of 22

(2) with no delivery of electrical current (sham, or control, group). For both groups, the stimulation current will gradually ramp up to 1mA during the first 60 seconds of stimulation but the current will only persist for real tDCS group.

Immediate Post-tDCS Assessment - Participants will complete the following assessments that were part of the Pre-tDCS assessment:

- 1. VAS. The Visual Analogue Scale
- 2. MFIS. Modified Fatigue Impact Scale
- 3. PSQI. Pittsburgh Sleep Quality Index
- 4. BDI. Beck Depression Inventory
- 5. PCS. Pain Catastrophizing Scale
- 6. MGPQ. McGill Pain Questionnaire
- 7. PVAQ. Pain Vigilance and Awareness Questionnaire
- 8. Resting state EEG.

Sessions 12 (1 week after), 13 (4 weeks after), 14 (12 weeks after) and 15 (24 weeks after) - Post Assessments (approximately 2.5 hours):

Post-assessments will take place at 1 week after, 4 weeks after, 12 weeks after and 24 weeks after the last tDCS session. Follow up-tDCS Assessment are:

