### 2. Study Design and Groups

- **Design:** Prospective, double-blind, randomized controlled trial with a parallel-group design. This prevents potential carry-over effects from sham to treatment phases.
- **Groups:**
  - **Active tDCS Group:** Real tDCS targeting the occipital nerve at 1.5mA for 20 minutes.
  - **Sham tDCS Group:** Sham tDCS with a brief current sensation to maintain blinding but no sustained current.

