### 3. Sample Size and Power

- **Primary Outcome:** Pain severity on the Visual Analogue Scale (VAS).
- **Secondary Outcomes:** Questionnaire measures (MFIS, PSQI, BDI, PCS, MGPQ, PVAQ) and neurophysiological measures (LEP, EEG, rsfMRI).
- **Sample Size:** 60 participants (30 per group), allowing an 80% power to detect a 1.1 cm difference on the VAS scale (Cohen's d effect size) with a significance level of 0.05. The design anticipates a 10% dropout rate.

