**Deviation statistical plan:**

The study was unfortunately disrupted due to the impact of COVID-19, which led to its discontinuation. Consequently, we have been limited in our ability to collect and analyze comprehensive data, and are currently only able to report descriptive statistics. We acknowledge that this is a limitation in our findings, and we are exploring potential avenues to resume the study and gather more robust data in the future.

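### No blocking or stratification is described behind the 30-per-group target, although baseline VAS is recorded before assignment; if allocation is unrestricted, chance gaps in baseline pain are large next to the 1.1 cm target

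*Protocol*

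**What the plan says.** **Allocation.** The protocol's Methods and Procedures, under the heading for Sessions 2 to 10, states: "Participants will be randomly assigned to two different groups after they have finished assessment". SAP section 2 adds only the design label: "Prospective, double-blind, randomized controlled trial with a parallel-group design". Neither document's readable text mentions a sequence method, blocks, strata, minimisation or concealment.

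**What is known at assignment.** The VAS is the first instrument listed for the Session 1 pre-treatment assessment, so each participant's baseline pain is on record before allocation.

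**Size.** SAP section 3 plans "60 participants (30 per group), allowing an 80% power to detect a 1.1 cm difference on the VAS scale", with alpha 0.05 and 10% dropout. It gives no SD.

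**Analysis.** SAP section 6A plans a repeated-measures ANOVA with group as the between-subjects factor. Baseline is one level of time, not a covariate. The closing deviation section says that COVID-19 led to discontinuation, that the investigators "are currently only able to report descriptive statistics", and that they are looking at ways to resume.

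**The concern.** Baseline pain is likely to be among the best predictors of later pain. Here it is measured before assignment, but no use of it in the assignment is described. With 60 participants planned, and fewer if the early stop cut enrolment short, chance alone can leave the arms apart in baseline pain by an amount that is not small beside the effect sought. Equal arm sizes are also not protected at an unplanned stop unless the list is blocked.

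At stake are precision and the comparability of the arms. This matters more once the report is descriptive, because a reader comparing arm summaries cannot readily separate a treatment difference from a starting difference.

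**Working it through.** **Inputs.** From SAP section 3: 30 per group, 80% power, difference 1.1 cm, alpha 0.05, 10% dropout. Assumptions: two-sided test; a baseline SD equal to the SD behind the power statement; 10 per arm (or 20 in all) for an early stop, since the number enrolled is not given; baseline-outcome correlation r = 0.5, also not given.

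**1. The plan's own figure.** N = 60 cannot be reproduced directly without an SD, so I solved for the SD it implies.
- 30 per arm analysed, noncentral t: d = 0.736, so SD = 1.1/0.736 = 1.49 cm. The normal approximation gives d = 0.723 and SD = 1.52 cm.
- 27 per arm after 10% dropout, normal approximation: d = 0.762, so SD = 1.44 cm. Then 54/0.9 = 60.
- Reading 1.1 as Cohen's d gives 13 per arm, which does not match 30.

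So N = 60 is attainable with an SD of about 1.44 to 1.52 cm, but it cannot be verified. I use 1.49.

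**2. Chance gap in mean baseline VAS, unrestricted allocation.** SE = SD × √(2/n); 95% range = ±1.96 × SE.

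| n per arm | SE (cm) | 95% range (cm) |
|---|---|---|
| 30 (planned) | 1.49 × √(2/30) = 0.38 | ±0.75 |
| 10 (assumed) | 1.49 × √(2/10) = 0.67 | ±1.31 |

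Across SD 1.44 to 1.52 the ranges are ±0.73 to ±0.77 cm and ±1.26 to ±1.33 cm. A gap above 0.55 cm, half the target, has probability 14% to 16% at 30 per arm and 39% to 42% at 10 per arm.

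**3. How much reaches the result.** With equal SDs at baseline and follow-up, a baseline gap D shifts the raw follow-up difference by rD and the change-score difference by −(1−r)D. At r = 0.5 both are D/2: 0.75/2 = 0.38 cm at the edge of the planned-size range, and 1.31/2 = 0.66 cm at 10 per arm. The group-by-time interaction compares changes, so it removes part of the gap. Covariate adjustment for baseline would remove essentially all of the linear part.

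**4. Arm sizes, unrestricted 1:1.**
- P(exactly 30:30) = 10.3%; P(35:25 or worse) = 24.5%.
- At an assumed stop after 20, P(13:7 or worse) = 26.3%.
- Power cost: 80.0% at 30:30 against 78.9% at 35:25. This part is minor.

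**5. What stratified blocks would gain.** A median split of a normal variable explains 2/π = 0.637 of its variance, and √(1 − 0.637) = 0.60, so perfect balance within strata would shrink the gap by 40%. I simulated normal VAS values with two strata and blocks of 4 or 6 in random order.
- Cut at the median: the 95% gap fell by 35% at N = 20 and 39% at N = 60.
- Cut 1 SD from the median: it fell by 17% and 24%.
- A block of size b leaves the arms at most b/2 apart in its stratum. With two strata the cap is 2 × 6/2 = 6, or 2 × 4/2 = 4 if no block exceeds 4.

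**The case against.** **Silence is not simple randomisation.** The protocol is an ethics-board form that asks for lay language, and an equal split of 30 and 30 fits a blocked list at least as well as coin-tossing. This stands. A reader might infer that nothing kept the arms balanced; the documents show only that no method is described. Every probability above is conditional on unrestricted allocation.

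**The planned test compares changes from baseline.** Correct, and a gap would therefore not pass whole into the primary test. Change scores still over-correct by (1−r)D, so the protection is partial. Nor does the deviation section say that the summaries will be unadjusted; descriptive statistics can include baseline values and mean change by arm.

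**The gap is ordinary sampling error already allowed for in the power calculation.** Also fair. At planned size and the implied SD, ±0.75 cm is below the 1.1 cm target. Only at the assumed smaller size does the range exceed it.

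**A larger SD would make the problem look worse.** It would, but an SD of 2.5 cm, for instance, gives only about 39% power at 30 per arm against the stated 80%. The documents do not support such figures.

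**No-shows after assignment.** A reader might infer that assigning straight after assessment lets people who never start stimulation dilute the intention-to-treat result through carried-forward baselines. The sentence sits under the stimulation sessions and fixes only the order, so it is compatible with assignment at Session 2. No no-show rate is given. The documents do not support that claim.

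**Enrolment has stopped.** A design change can help only resumed enrolment, which is being explored and not planned.

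**Conclusion.** The point holds in a limited form. The documents describe no restriction on randomisation, and no use of the recorded baseline VAS in it. If allocation is unrestricted, the comparison remains unbiased, but the baseline-pain gap has a 95% range of about ±0.75 cm at 30 per arm and about ±1.3 cm at an assumed 10 per arm, against 1.1 cm. The planned analysis removes part of such a gap; descriptive summaries may not.

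This is a matter of chance imbalance and precision, not of systematic bias, and unequal arm sizes contribute little. The figures rest on the SD implied by the power statement applying to baseline VAS, and the smaller trial size is an assumption. The change is worth making if the study resumes, and the reporting step is worth taking now.

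**What to change.** **Any resumed enrolment.** Replace the allocation sentence with wording such as: Participants are assigned 1:1 from a concealed computer-generated list in permuted blocks of varying size, stratified by Session 1 VAS at a pre-set cut. Set the cut near the expected median, because about half the gain is lost if it is 1 SD off. In SAP section 6A, adjust the VAS model for the stratum, or preferably for baseline VAS itself.

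**Data in hand.** Report the allocation method actually used, the number assigned to each arm, and baseline VAS and change from baseline by arm. If a blocked or stratified list was used, saying so settles the design question.

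**Cost.** A protocol sentence, a line in the SAP, and two lists in place of one. Small blocks are slightly predictable to anyone who learns an allocation, which matters in a single-laboratory sham trial. Avoid blocks of 2 and keep the block sizes from the staff who enrol and treat.

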
Last Revised 01/2016 Page 4 of 22

Given the promising results for pain symptoms in fibromyalgia patients, we aim to explore this treatment option for Gulf War illness patients with pain symptoms

What information do you expect to obtain and how will the obtained knowledge be applied:

To investigate the effects of repeated sessions of tDCS targeting the occipital nerve field on pain symptoms and on global and specific symptoms in GWI participants, we will measure possible changes in symptoms (using questionnaires) and electrophysiological brain activity (resting-state EEG) in a group that receives active tDCS and a group that receives sham tDCS.

The primary outcome measure for pain symptoms will be measured by the Visual Analogue Scale (VAS).

VAS. The Visual Analogue Scale consists of a straight line of 10 cm with the endpoints defining extreme limits such as 'no pain at all' and 'pain as bad as it could be'. The patient is asked to mark his widespread muscle pain level on the line between the two endpoints. The distance between 'no pain at all' and the mark then defines the subject's pain. VAS will be assessed for pain severity. It has been used to measure symptom relief and treatment satisfaction. Several studies have demonstrated that the VAS is sensitive to treatment effects (Haefeli & Elfering, 2006). The VAS has been found to correlate positively with other self-reporting measures of pain intensity. In addition, the difference in pain intensity measured at two different points of time by VAS represents the real difference in magnitude of pain which seems to be the major advantage of this tool compared to others. This will be performed both during Phase I as well as during Phase II after 4-weeks, 12-weeks, and 24-weeks of treatment.

The secondary outcome measures will include measures of of global change as well as changes in specific symptoms of interest related to the Center for Disease Control (CDC) clusters, as GWI is a complex disease with multiple symptom manifestations: Cluster A by the Modified Fatigue Impact Scale (MFIS) and the Pittsburgh Sleep Quality Index (PSQI); Cluster B, mood and cognition, will be assessed by Beck Depression Inventory (BDI); and Cluster C by the Pain Catastrophizing Scale (PCS), McGill Pain Questionnaire (MGPQ), and Pain Vigilance and Awareness Questionnaire (PVAQ).

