Payment for Participation

Will par	rticipants be paid an incentive for participation in research?
	⊠Yes □No
	If yes, please complete the following (mark all that apply):
	SONA system credit(s)
	Cash
	Gift card
	Other:
	Please note: 1) payment amount; 2) payment schedule; 3) will the incentive be pro-rated based on participant's early withdrawal?
	Human subjects will receive a total amount of \$250 for completing all visits. After the last treatment session at visit 11 they will receive \$100 and at the end of the follow-up phase of the study, they will receive \$150.
Will par	rticipants be reimbursed for parking, travel, or other expenses related to participation in the research?
	☐ Yes ⊠ No
	If yes, please describe:

Last Revised 01/2016 Page 11 of 22

INFORMED CONSENT

In research involving more than minimal risk, when capacity to consent is unclear, the capacity to consent must be determined by a physician, clinical psychologist, or by other qualified professionals. Individuals who lack the capacity to consent may participate in research only if consent is given on their behalf by a legally authorized representative.

Will you obtain written, signed informed consent from each participant/participant's representative? ⊠ Yes □ No
Will your study involve the use of any language other than English for Informed Consent forms, data collection instruments or recruitment materials?
☐ Yes
If "Yes," after the IRB has notified you of the approval of the English version of your forms, you must then submit the foreign language versions along with an English translation for each.
Specify all foreign languages:
Who will be authorized to obtain informed consent? Identify by name and training the individual(s) authorized to describe the research and obtain consent form from participants or their legal representatives. [name]. – Associate Professor in BBS, study PI [name] research scientist in BBS [name], M.A doctoral student
Please see the descriptions above for the qualifications of [name], [name], and [name]
Will the participants be informed about which information is recorded and stored? ☑ Yes ☐ No
If no, explain:
Who will provide written informed consent/permission/assent? (Attach copies of all versions that will be used) ☐ Adult Participants (him/herself) ☐ Legally Authorized Representative ☐ Parents (Permission for Minor)
Children (Assent)

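### At weeks 4, 12 and 24 the self-marked pain VAS is scheduled only within an EEG visit of about 2.5 hours; a home form for non-attenders would cheaply replace values the SAP would otherwise fill in

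*Protocol*

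**What the plan says.** The protocol states that "The primary outcome measure for pain symptoms will be measured by the Visual Analogue Scale (VAS"). The VAS is a mark the participant places on a 10 cm line, so it needs paper and a pen.

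The methods section plans four follow-up sessions after the last stimulation, at weeks 1, 4, 12 and 24 (Sessions 12 to 15). The entry ends "14 (12 weeks after) and 15 (24 weeks after) - Post Assessments (approximately 2.5 hours"). One list of eight items serves all four: the VAS, six questionnaires and resting-state EEG. Seven are self-report. Only the EEG needs equipment: a 64-electrode cap that takes up to 30 minutes to place, and a 5-minute recording. Neither document describes a postal, telephone, online or shortened-visit route for the VAS. The telephone appears only in recruitment and screening.

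Under Payment for Participation, the form asks whether participants will "be reimbursed for parking, travel, or other expenses related to participation in the research"; the answer is no. The same section pays $150 of the $250 at the end of follow-up.

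The SAP's timeline and primary model use baseline, immediate post-treatment and weeks 4, 12 and 24, but not week 1. On missing data, SAP section 3 says "The design anticipates a 10% dropout rate", section 6A applies LOCF to the intention-to-treat analysis, and section 9 calls for multiple imputation above 10% missing and a comparison with and without LOCF.

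**The concern.** The trial's first aim is a lasting effect on pain, and three of the five time points in the primary model are follow-ups. As written, the simplest measurement in the study depends on attending for its most demanding one. The participants have chronic pain, often with musculoskeletal disability, so missing a visit may plausibly depend on pain itself.

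The plan deals with a missed VAS only at the analysis stage. For someone last seen at the end of treatment, LOCF enters that early value as the week-24 result. This assumes that any benefit persisted, which is the question the week-24 comparison is meant to answer. Multiple imputation avoids that assumption but still needs a model for why the value is absent. An observed value needs neither.

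**Working it through.** **Inputs from the SAP.** Section 3 gives "60 participants (30 per group), allowing an 80% power to detect a 1.1 cm difference on the VAS scale", a significance level of 0.05 and 10% dropout. It gives no SD and does not say whether the test is two-sided. Section 9 triggers multiple imputation above 10% missing.

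**Assumptions, since the documents give no figures.** 10%, 20% or 30% of participants miss the visit in question, and home forms recover half to three-quarters of the missed values.

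**1. The plan's own figure.** Without an SD, the 60 cannot be reproduced. Solving backwards, two-sided, normal approximation: SD = 1.1 / [(1.960 + 0.842) × √(2/n)].
- n = 27 per group (60 less 10%): 1.1 / (2.802 × 0.2722) = 1.44 cm.
- n = 30 per group: 1.1 / (2.802 × 0.2582) = 1.52 cm.

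The stated size therefore fits an SD of about 1.44 cm with 54 evaluable (54 / 0.9 = 60).

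**2. Complete-case standard error at one visit.** With equal groups the SE is proportional to 1/√n, so the ratio is √(n without home forms / n with home forms). The SD cancels.

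| Missed | Observed without | Observed with (half; three-quarters) | SE ratio | SE reduction | Still missing |
|---|---|---|---|---|---|
| 10% | 54 | 57; 58.5 | √(54/57) = 0.973; √(54/58.5) = 0.961 | 2.7%; 3.9% | 5%; 2.5% |
| 20% | 48 | 54; 57 | √(48/54) = 0.943; √(48/57) = 0.918 | 5.7%; 8.2% | 10%; 5% |
| 30% | 42 | 51; 55.5 | √(42/51) = 0.907; √(42/55.5) = 0.870 | 9.3%; 13.0% | 15%; 7.5% |

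At 20% missed, recovery brings the rate to or below the 10% trigger. At 30% missed with half recovered, 15% remains missing and the trigger still applies.

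**3. Power for the same comparison.** Power = Φ(1.1 / [SD × √(2/n)] − 1.96), with n per group and the back-solved SD of 1.44 cm. It is 80%, 75% and 70% at 10%, 20% and 30% missing (n = 27, 24, 21). Recovery raises 75% to about 80-82% (n = 27 to 28.5) and 70% to about 78-81% (n = 25.5 to 27.75).

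**4. Multiple imputation or a likelihood mixed model.** Earlier VAS values already recover part of the information. Approximately, the variance is proportional to (1 − R²)/n_obs + R²/60, where R² is the share of week-24 variance explained by earlier visits. R² is assumed to be 25-50%.
- 10% missed, smallest gain (R² = 0.50, half recovered): √[(0.5/57 + 0.5/60) / (0.5/54 + 0.5/60)] = 0.986, a 1.4% reduction.
- 10% missed, largest gain (R² = 0.25, three-quarters recovered): √[(0.75/58.5 + 0.25/60) / (0.75/54 + 0.25/60)] = 0.970, a 3.0% reduction.
- 30% missed, by the same formula: 5.3% (51 against 42 observed, R² = 0.50) to 10.4% (55.5 against 42, R² = 0.25).

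**5. LOCF.** All 60 contribute, so step 2 does not describe this analysis; the issue is bias. In each arm the bias is the fraction filled in times the mean gap between the carried value and the true one. As an illustration only, suppose active-arm non-attenders had a 1.1 cm benefit at their last visit and have lost all of it by week 24, while sham non-attenders are unchanged. Durability is then overstated by 0.10 × 1.1 = 0.11 cm at 10% missed and 0.30 × 1.1 = 0.33 cm at 30%. If recovered participants resemble the others, home forms cut this to 0.03-0.06 cm and 0.08-0.17 cm. If benefit grew after the last visit, the bias would run the other way.

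**The case against.** Much of the case on the other side stands.

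- The absence of a home route is silence in the documents; nothing prohibits one. The place of Sessions 12 to 15 is not restated; attendance is inferred from the EEG, the visit length and Session 1 being at the laboratory. Nothing makes the VAS conditional on the EEG.
- Some features favour retention: the $150 paid at the end of follow-up, recruitment in North Texas, and recruitment partly from earlier participants who agreed to stay in contact. No attendance data show that visit length causes missed visits.
- The SAP's 10% is dropout, which can include people who have withdrawn. Recovering half to three-quarters of them may be optimistic.
- Sending home every questionnaire would include the BDI. The protocol's section on staff qualifications has trained staff monitor assessment materials for depression and suicidal ideation, and postal return would delay that review.

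Three stronger readings are tempting but unsupported. A reader might infer that a missed visit costs the participant's primary outcome altogether. It does not: only that visit's VAS is lost, baseline and any other attended visits remain, and the participant stays in the intention-to-treat analysis. A reader might count all four follow-ups as affected, but week 1 is not in the primary model. A reader might also take the SAP's closing statement, "The study was unfortunately disrupted due to the impact of COVID-19, which led to its discontinuation", as proof that VAS data were lost for want of a remote route. It does not say that. It shows only that the change could still be used if the study resumes, which the sponsor says it is exploring.

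The scheduling fact remains, with no alternative described and a missed value dealt with only in the analysis.

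**Conclusion.** The point holds as a cheap improvement to data collection at weeks 4, 12 and 24; it does not show a flaw that undermines the trial. Near the SAP's 10% allowance the gain is small: a complete-case SE about 3-4% lower, or about 1.4-3% under multiple imputation or a likelihood model. If 30% of visits were missed, the gain would be material: 9-13% complete-case, or about 5-10% with modelling. Under the planned LOCF analysis the benefit is mainly less bias in the long-term comparison, and its size depends on how pain changes after the last attended visit. All these figures rest on assumed attendance, recovery and R² values. The power figures also rest on a back-solved SD.

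**What to change.** Add to Sessions 13 to 15, and optionally Session 12, that a participant who cannot attend marks the same pre-printed 10 cm VAS at home on the due date and returns it by prepaid post. Only the EEG then counts as missed. Laboratory completion stays the default.

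Record the place of completion at each visit, and state in the SAP that results will be reported with and without home forms. The SAP should note that this comparison mixes setting with selection: dropping home forms also drops the people who could not attend, so it cannot isolate a setting effect.

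The other questionnaires may be added to the home pack, but home completion of the BDI must first be reconciled with the protocol's staff monitoring of assessment materials. The VAS can proceed without waiting for that.

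The cost is a short amendment, postage, form handling and a small possible setting effect. It would apply only if the study resumes.
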